## 6. METHODS

## 6.1 Study parameters/endpoints

## 6.1.1 Main study parameter/endpoint

The main study parameter is the level of the patient's dysfunctioning, measured by the Outcome Questionnaire-45 (OQ-45). Data from session-to-session measurements will be analysed using multilevel modelling. A maximum of 15 sessions was chosen to be analysed. The average amount of sessions is around 9 in the participating centers, but ranges from 1 to more than 100 sessions. If patients are measured until the end of treatment, the longer treatments will have too much influence in the model (because they have more measurement points). As a result, the model is no longer representative for brief treatments. Approximately /4 of treatments are done in 15 sessions, and that is why this number was chosen as a basis for data analysis.

## 6.1.2 Secondary study parameters/endpoints

Two follow-up measures are included in the study design: one at three months and one at six months after treatment termination or 15 sessions of treatment. Another secondary study parameter includes the percentage of treatment drop-outs in each reseach condition.

#### 6.1.3 Other study parameters

Other study parameters include initial severity on the OQ-45 at start of treatment, diagnosis on Axis I and II of the DSM-IV, gender, age and previous treatment for patients. Therapist factors that are studied are: gender, age, years of experience, use of the feedback, therapist expectation of outcome, internal and external feedback propensity and therapist's attitude towards using the feedback.

#### 6.2 Randomisation, blinding and treatment allocation

Patients are randomly assigned to one of the three research conditions. The randomization procedure is build in the software used to provide feedback and is completely random. The researcher is aware of the treatment condition of the patients, but cannot influence it. By the nature of the intervention, therapists are aware of the research condition of their patients.

## 6.3 Study procedures

#### Patient measurements

*Outcome Questionnaire-45 item version (OQ-45).* The Dutch translation of the Outcome Questionnaire-45 item version (OQ-45) is used to measure patient progress during treatment. The OQ-45 is a self-report instrument and has 45 items, 9 of which are

reversed, asking how the respondent has felt over the last week on a 5 point rating scale, ranging from 0 (never) to 4 (almost always). The OQ-45 consists of three subscales that are aimed at assessing different domains of client functioning: Symptom Distress, Interpersonal Relations and Social Role. The Symptom Distress domain consists 25 items relating to psychological symptoms that are common in highly prevalent mental disorders. The Interpersonal Relations domain consists of 9 items that assess the functioning of the patient in interpersonal relationships, and the Social Role domain assesses the patients functioning in social roles, such as work and school. The Dutch OQ-45 has appropriate psychometric properties. The internal consistency for the Total score ranges between 0.92 and 0.96 in university, community, patients and community and patients combined samples. For the subscales the international consistency is 0.90-0.95 for the Symptom Distress scale, 0.74-0.84 for the Interpersonal Relations subscale and 0.53-0.72 for the Social Role subscale (de Jong, Nugter, Lambert & Burlingame, 2008). An additional factor that measures Anxiety and Somatic Distress was found, that can be used as separately from the three factor structure. This factor had an internal consistency ranging from 0.79 to 0.89 (de Jong et al, 2007).

*Mini International Neuropsychiatric Interview (MINI)*. The Mini International Neuropsychiatric Interview (MINI) Plus 5.0.0.-R is used to screen for Axis-I disorders. The MINI is a short clinical diagnostic interview developed to explore the presence of Axis-I disorders according to the DSM-IV diagnostic criteria (Sheehan et al., 1998). The MINI-Plus is an extended version of the original MINI. Lecrubier and colleagues (Lecrubier et al., 1997) report sufficient reliability; inter-rater reliability ranged from k = 0.88 to 1.00, testretest reliability ranged from 0.76 to 0.93, validity was demonstrated by sufficient concordance with the Composite International Diagnostic Interview (CIDI, WHO). In this study the assessment of current psychopathology was used. The Dutch translation of the MINI-Plus 5.0.0-R was used in an electronic version (Van Vliet et al., 2000). The MINI is part of the standard intake procedure on all three research locations.

Assessment for Signaling Clients (ASC). The Assessment for Signaling Clients (ASC) is used to measure the therapeutic alliance, motivation for treatment, social support and stressful life events. The ASC consists of 40 items that are scored on a five point rating scale, ranging from 1 (strongly disagree) to 5 (strongly agree). All subscales have a cutoff score that indicates if that factor is problematic in the patient. In addition, each item has an individual cutoff score indicating when the score on that item is problematic. The Alliance subscale consists of 11 items that assess the alliance in the session with the therapist prior to assessment. An example item is "I felt I could trust my therapist completely". The Social Support subscale consists of 11 items that assess the support that the patient felt outside of therapy. An example item of this scale is "I could talk about problems with my friends". The motivation subscale consists of 9 items and assesses the patient's motivation for therapy. An example item is "I don't think therapy will help me feel any better". The Life Events subscale assesses life events in the past week, that may have influenced the patient's functioning and consists of 9 items. An example item is "I felt rejected or betrayed by someone". The ASC has been translated into Dutch. A pilot study to assess its psychometric properties is currently being performed.

*Demographic questionnaire*. The demographic questionnaire is a 19-item self-constructed questionnaire that assesses the demographic characteristics of the patient. It asks for the patient's date of birth, gender, postal area code, nationality, land of birth, land of birth of the patient's parents, marital status, living and working situation, educational level, prior treatment, pretreatment use of medication, the main complaint and the duration of the main complaint.

## Therapist measurements

Feedback User Quesionnaire. A feedback user questionnaire will be administered to the therapists every six months and consists of the External Feedback Propensity Scales and an adaptation of the CFIT User Survey. The External Feedback Propensity Scale (EFPS; Herold et al, 1996) is being used to measure external feedback propensity. External feedback propensity reflects the preference for externally mediated feedback as well as greater faith in information that one can self-generate. The scale consists of six items that are answered on a five-point rating scale that varies from strongly disagree to strongly agree. An item from the External Propensity scale is 'It is very important to me to know what people think of my work'. An adaptation of the CFIT User Survey, designed by the Center for Evaluation and Program Improvement of Vanderbilt University, will be used to measure goal commitment, therapy related self-efficacy and perceived validity of the feedback. The items are scored on various five-point rating scales. The goal commitment scale exists of seven items and is based on the Goal Commitment Scale (Hollenbeck & Klein, 1987). A sample item is 'It is hard to take the idea of using these measures in my clinical practice seriously'. The therapy related self-efficacy scale consists of eight items and was constructed according to Bandura's guidelines of how to develop domain-specific self-efficacy scales (Bandura, 1997). A sample item from that scale is 'To what extend do you feel confident in your ability to know what to do if a client is not progressing in treatment'. Perceived validity of the feedback will be measured by a six-item scale, that was self-constructed by Vanderbilt University. A sample item from that scale is: 'I think that feedback based on the OQ-45 will be helpful for my counseling'. In a previous study amongst 47 therapists, internal consistency values were 0.90 for the goal commitment scale, 0.87 for the perceived validity scale and 0.83 for the self-efficacy scale.

*Expectation of Outcome Questionnaire (EOQ).* A self-contructed questionnaire will be used to measure therapist's expectation of their patient's treatment outcome. This two item questionnaire assesses 1) How much progress the therapist thinks the patient has made since the start of treatment and 2) What treatment outcome the therapist expects for this patient (deterioration, no change, improvement, recovery) at the end of treatment.

*Use of Feedback (UOF)*. A self-constructed questionnaire assesses what the therapist has done with the feedback. The first item assess to what extend the feedback was in concurrence with what the therapist expected. The second item assesses if the therapist discussed the feedback with the patient and the third item assesses what the therapist has done with the feedback as a result of the feedback.

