#### **Procedure**

All patients that asked to participate in this study will be interviewed with the MINI Plus as part of the standard intake procedure. After patients agree to participate the research assistant will adminster the SCID-II PQ. As from start of treatment, participants will be asked to complete the OQ-45 before each session, for a maximum of 15 sessions and/or one year. In addition, the OQ-45 will be administered 3 and 6 months after treatment (or study) termination. In the ETR feedback condition, patients will fill out the ASC when they are going off track. In the ROM feedback condition and control condition, patients will fill out the ASC when they would have signalled, but the therapist will receive no feedback on how the patient responded.

Therapists will be asked to complete the EOQ on each of their patients at sessions 1, 5, 10 and 15 or the end of treatment, if this is within 15 sessions. The UOF will be administrated after sessions 5, 10 and 15 or the end of treatment. To measure therapists' attitude towards getting feedback, the CFITUS will be administered before the start of the study, after six months, after one year and after a year and a halve. At the first administration, before the start of the study, the EFPS and GSE will be filled out by the therapists as well.

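### Therapists forecast the outcome at the end of treatment, but for about a quarter of patients no OQ-45 is scheduled at that time

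*Protocol*

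**What the plan says.** Secondary objective 1 (Protocol section 2) asks whether therapists can predict their patients' progress accurately, with or without feedback. The instrument is the two-item EOQ, which the study team built itself (section 6.3, Therapist measurements).

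- Item 1 assesses "How much progress the therapist thinks the patient has made since the start of treatment".
- Item 2 assesses "What treatment outcome the therapist expects for this patient", in four categories from deterioration to recovery, with the end of treatment as horizon.

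The schedule is in section 6.3, Procedure: "Therapists will be asked to complete the EOQ on each of their patients at sessions 1, 5, 10 and 15 or the end of treatment", the last alternative applying when treatment ends within 15 sessions.

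The outcome is measured on a different clock. Under Procedure, patients are to "complete the OQ-45 before each session, for a maximum of 15 sessions and/or one year", and afterwards "the OQ-45 will be administered 3 and 6 months after treatment (or study) termination". Section 6.1.2 places the two follow-ups "after treatment termination or 15 sessions of treatment". Section 6.1.1 gives the reason for the limit ("A maximum of 15 sessions was chosen to be analysed"): about three quarters of treatments finish within that number, the mean is around 9 sessions, and the range goes beyond 100.

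**The concern.** A forecast can be judged only against the state it refers to. If treatment finishes within the measurement period, the last OQ-45 lies close to the end of treatment and the two match. If it runs past session 15, the therapist has forecast a state at an unspecified later date for which no OQ-45 is planned.

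This belongs to data collection. A later analysis plan can choose a comparator, but it cannot supply a score that was not collected, nor turn an end-of-treatment forecast into a session-15 forecast. For the longer treatments it could only compare the forecast with a score from another time, or leave those patients out. Leaving them out would select on treatment length, which is known only after randomisation. If feedback altered treatment length, the selection could then differ between arms. The protocol does not say that it does, so this is a risk and not a finding.

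At stake is the forecasting part of one of the trial's two secondary objectives.

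**Working it through.** **Inputs**
- Target sample size: 600 (section 4.4).
- Share of treatments finished within 15 sessions: about 3/4 (section 6.1.1).
- Mean treatment length: about 9 sessions (section 6.1.1).
- Three arms, randomised at patient level (sections 5.1 and 6.2).

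**The plan's own figure.** Section 4.4 takes 4 × 90 = 360 patients and a design effect of 1 + 3 × 0.18 = 1.54. Then 1.54 × 360 = 554.4. The stated 554 is reproduced, and the plan rounds it up to 600.

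**The input of 3/4.** It cannot be reproduced, because the distribution of session numbers is not given. It is compatible with the stated mean. If a quarter of treatments had just 16 sessions, they would contribute 0.25 × 16 = 4.0 to the mean of 9. That leaves 5.0 / 0.75 = 6.7 sessions on average for the rest. Longer long treatments would lower the 6.7.

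**Patients without an OQ-45 at the forecast time**
- Share: 1 − 0.75 = 0.25.
- Of 600: 0.25 × 600 = 150, or 150 / 3 = about 50 per arm.
- Of 554: 0.25 × 554 = 138.5, or about 139.
- If the share finishing is 80%: 0.20 × 600 = 120. If it is 70%: 0.30 × 600 = 180.

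Patients who reach one year before session 15 and continue would add to these numbers. The protocol gives no figure for them.

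**Time points side by side**

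| | Treatment within the measurement period | Treatment beyond session 15 |
|---|---|---|
| Item 1 refers to | the session of completion | the session of completion |
| OQ-45 for item 1 | same session | same session |
| Item 2 refers to | end of treatment | end of treatment, after session 15 |
| OQ-45 for item 2 | last in-treatment score | none scheduled at that time |
| Follow-ups counted from | end of treatment | session 15 or study termination |

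The mismatch sits in one row of one column: item 2 in the longer treatments.

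**Counted by forecast.** Patients in long treatments are still there at every EOQ session, while others leave earlier, so the affected share rises over the schedule. At session 10 it is 0.25 divided by the proportion who reach session 10. The protocol does not give that proportion. If it is assumed to be 60%, the share is 0.25 / 0.60 = 42%. If it is 40%, the share is 0.25 / 0.40 = 63%. At session 15, item 2 has no scheduled end-of-treatment OQ-45 for any patient who continues.

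**The case against.** The best defence has four parts.

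- **No scoring rule is fixed.** The protocol does not say which EOQ item is compared with which OQ-45 score, and section 8.2 covers only the OQ-45 model. An analysis plan may define the comparison. This stands. A reader might infer that secondary objective 1 will be scored wrongly, but the protocol does not say so. What remains is that no rule can score item 2 at its stated horizon in the longer treatments.
- **The OQ-45 does not stop altogether at session 15.** It is repeated 3 and 6 months later, and a treatment that ends around then has a score near its end. This stands in part. It rules out saying that these forecasts can never be checked. But the follow-ups are dated from session 15 or study termination, so they meet the end of a longer treatment only by coincidence.
- **Item 1 is unaffected.** The objective speaks of progress, and item 1 can be set against the OQ-45 of the same session in every patient. This stands, so part of the objective is served. Item 1 judges progress so far, however, and is not a forecast.
- **The limit of 15 sessions is deliberate.** Section 6.1.1 explains that long treatments would otherwise weigh too heavily in the model. This stands too. The limit need not change. The item wording can be brought into line with it.

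Reporting short and long treatments separately, with the follow-up scores as a sensitivity analysis for the latter, would soften the problem but not remove it.

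**Conclusion.** The point holds in a limited form. Item 2's horizon is not aligned with the OQ-45 schedule for about 25% of patients, or about 150 of 600 (120 to 180 for shares finishing of 80% to 70%). In these patients the forecast part of secondary objective 1 cannot be checked at the time the therapist was asked about. Item 1, the primary endpoint, the primary analysis and the sample size are unaffected.

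The size rests on two assumptions: that the three-quarters figure is right, and that it carries over from the centres' treatments to the trial's patients.

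A reader might want to go on and state what share of forecasts would be misjudged. The documents do not support a figure. They give no rate of change in outcome category after session 15 and no accuracy of therapists' forecasts for this comparison, and errors could run both ways. Nor do they say that long treatments are the difficult ones, or that they will be dropped.

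The protocol describes what item 2 assesses and does not reproduce the form. If the form already limits the horizon to the study period, only the description needs correcting.

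This is a cheap improvement and not a threat to the trial's main conclusion.

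**What to change.** Before the start:

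1. Word item 2 as the expected outcome at the end of the OQ-45 measurement period: session 15, one year or the end of treatment, whichever comes first. The one-year limit must be named, or patients who reach it before session 15 remain misaligned.
2. Compare item 2 with the last in-treatment OQ-45.
3. At session 15, for patients who continue, ask only item 1, or ask for the expected state at the 3-month follow-up, which is measured.

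The cost is rewording one item of a form the study team built itself. The small downside is that the result describes prediction within the study period and not over the whole of long treatments.

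If the end-of-treatment question matters more, the alternative is to keep item 2 and add one OQ-45 at the true end of treatment. That costs one more questionnaire for these patients (18 instead of the 17 in section 9.3). With treatments of more than 100 sessions, some of these scores could also come late for a two-year study.

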#### **Procedure**

All patients that asked to participate in this study will be interviewed with the MINI Plus as part of the standard intake procedure. After patients agree to participate the research assistant will adminster the SCID-II PQ. As from start of treatment, participants will be asked to complete the OQ-45 before each session, for a maximum of 15 sessions and/or one year. In addition, the OQ-45 will be administered 3 and 6 months after treatment (or study) termination. In the ETR feedback condition, patients will fill out the ASC when they are going off track. In the ROM feedback condition and control condition, patients will fill out the ASC when they would have signalled, but the therapist will receive no feedback on how the patient responded.

Therapists will be asked to complete the EOQ on each of their patients at sessions 1, 5, 10 and 15 or the end of treatment, if this is within 15 sessions. The UOF will be administrated after sessions 5, 10 and 15 or the end of treatment. To measure therapists' attitude towards getting feedback, the CFITUS will be administered before the start of the study, after six months, after one year and after a year and a halve. At the first administration, before the start of the study, the EFPS and GSE will be filled out by the therapists as well.

## 6.4 Withdrawal of individual subjects

Subjects can leave the study at any time for any reason if they wish to do so without any consequences. The investigator can decide to withdraw a subject from the study for urgent medical reasons, or if the patients diagnosis or treatment is changed in such a way that the patient no longer fits the inclusion criteria of the study.

## 6.5 Replacement of individual subjects after withdrawal

If patients withdraw from the study, the data used up until the moment of withdrawal will be used in analysis. No additional subjects will be included.

## 6.6 Follow-up of subjects withdrawn from treatment

Patients that withdraw from treatment (drop-outs) will not be followed-up.

## 6.7 Premature termination of the study

Premature termination of the study is highly unlikely, but in case it will occur (for instance if a reorganization in one of the treatment centers occurs) it will not have unwanted effects for the patient. Patients will be informed of study termination and thanked for their participation.

## 7. SAFETY REPORTING

#### 7.1 Section 10 WMO event

In accordance to section 10, subsection 1, of the WMO, the investigator will inform the subjects and the reviewing accredited METC if anything occurs, on the basis of which it appears that the disadvantages of participation may be significantly greater than was foreseen in the research proposal. The study will be suspended pending further review by the accredited METC, except insofar as suspension would jeopardise the subjects' health. The investigator will take care that all subjects are kept informed.

#### 7.2 Adverse and serious adverse events

Adverse events are defined as any undesirable experience occurring to a subject during a clinical trial, whether or not considered related to the investigational intervention. All adverse events reported spontaneously by the subject or observed by the investigator or his staff will be recorded.

A serious adverse event is any untoward medical occurrence or effect that at any dose results in death;

- is life threatening (at the time of the event);
- requires hospitalisation or prolongation of existing inpatients' hospitalisation;
- results in persistent or significant disability or incapacity;
- is a congenital anomaly or birth defect;
- is a new event of the trial likely to affect the safety of the subjects, such as an unexpected outcome of an adverse reaction, lack of efficacy of an IMP used for the treatment of a life threatening disease, major safety finding from a newly completed animal study, etc.

All SAEs will be reported to the accredited METC that approved the protocol, according to the requirements of that METC.

#### 7.2.1 Annual safety report

In addition to the expedited reporting of SUSARs, the sponsor will submit, once a year throughout the clinical trial, a safety report to the accredited METC, competent authority, Medicine Evaluation Board and competent authorities of the concerned Member States.

This safety report consists of:

- a list of all suspected (unexpected or expected) serious adverse reactions, along with an aggregated summary table of all reported serious adverse reactions, ordered by organ system, per study;
- a report concerning the safety of the subjects, consisting of a complete safety analysis and an evaluation of the balance between the efficacy and the harmfulness of the medicine under investigation.

